10.1.1.2 Vomiting Study Responder (V-SR)

For the primary efficacy responder parameter V-SR, the proportion of responders in the RLM group and the placebo group will be analyzed by the Cochran-Mantel-Haenszel (CMH) test controlling for geographic region. The number, percentage, and the 95% confidence interval for the percentage of Responders by treatment group, the difference in responder rates between the RLM and the placebo group and its corresponding 95% confidence interval, and the 2-sided p-value associated with the above CMH test will be presented. The Mantel-Haenszel estimate of odds ratio (RLM divided by Placebo) - controlling for geographic region- and the corresponding 95% confidence interval will also be provided.

A participant will be considered a vomiting study non-Responder (ie not a V-SR) if the weekly number of vomiting episodes is missing for any of the last 6 weeks of the 12-week Treatment Period.

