7.3. Method of Treatment Assignment

All participants will be centrally assigned to randomized study treatment using an interactive web response system (IWRS). Before the study is initiated, the log-in information and directions for the IWRS will be provided to each site.

At the beginning of the 12-week Treatment Period, eligible participants will be randomized in a 1:1 ratio to blinded treatment with relamorelin 10 µg or placebo. Randomization will be stratified by geographic region.

Study treatment will be dispensed at the study visits indicated in the Schedule of Activities (SoA) (Section 2).

Returned study treatment should not be re-dispensed to the participants.

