10.3.1. Key Statistical Methodology

The methodologies defined in [Table 10-2](#) apply as specified to individual endpoints defined in this protocol. All statistical tests will be 2-sided hypothesis tests performed at the 5% level of significance for main effects. All CIs will be 2-sided 95% CIs, unless stated otherwise.

Table 10-2: Statistical Methodology

Methodology	Description
Categorical counts	
 Number of participants in individual categories 
 Participants with ≥ 1 qualifying event counted once per individual category
Categorical descriptives	
 Number and percentage of participants in individual categories 
 Participants with ≥ 1 qualifying event counted once per individual category N1 if percentage denominator \neq number of participants in the population (standard percentage denominator) 
 N1 = participants with nonmissing baseline value
Event descriptives	
 Number and percentage of events in individual categories 
 Events counted individually for each instance Percentage denominator = total number of events
Continuous descriptives	
 N1, mean, SD, median, minimum, maximum N1 = participants with nonmissing value
CFB descriptives	
 Continuous descriptives for baseline, postbaseline, and change from baseline (CFB) values N1 = participants with nonmissing values at both baseline and the specified postbaseline analysis visit
Responder	
 Categorical descriptives for responders and nonresponders 
 Nonresponders include: 
 Participants who do not meet responder criteria Participants with no postbaseline values Risk differences and Wald CIs vs [placebo/active comparator] Estimates derived from Cochran-Mantel-Haenszel (CMH) model controlling for factors (treatment group, region) 
 Mantel-Haenszel (MH) odds ratios (ORs) and CIs vs placebo P-values comparing treatment group vs placebo N1 = all participants unless otherwise specified

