10.2 Secondary Efficacy Parameters

There are four secondary efficacy parameters, which are all defined for the last 6 weeks of the 12-week Treatment Period, as follows:

- **Nausea responder:** a study participant is considered a nausea responder for the study if he/she has an improvement of ≥ 2 -points in the weekly nausea symptom score for each of the last 6 weeks during the 12-week Treatment Period.
- **Abdominal pain responder:** a study participant is considered an abdominal pain responder for the study if he/she has an improvement of ≥ 2 -points in the weekly abdominal pain symptom score for each of the last 6 weeks during the 12-week Treatment Period.
- **Bloating responder:** a study participant is considered a bloating responder for the study if he/she has an improvement of ≥ 2 -points in the weekly bloating symptom score for each of the last 6 weeks during the 12-week Treatment Period.
- **Postprandial fullness responder:** a study participant is considered a postprandial fullness responder for the study if he/she has improvement of ≥ 2 -points in the weekly postprandial fullness symptom score for each of the last 6 weeks during the 12-week Treatment Period.

If a participant does not have individual item data for a particular symptom during any of the last 6 weeks of the 12-week Treatment Period, then the participant will not be considered a study responder for that symptom.

The proportion of responders in the RLM treatment group and placebo group for each secondary efficacy parameter will be analyzed using the analysis method as described for the V-RS primary parameter (Section 10.1.1.2).

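### The vomiting-responder rate difference has no stated region adjustment for its 95% interval, although randomisation, the CMH test and the odds ratio are all stratified by region

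*SAP*

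**What the plan says.** Protocol 7.3: "Randomization will be stratified by geographic region". SAP 16.11 lists the regions (seven, reading Middle East and Africa as one) and pools any with fewer than 8 participants who have post-baseline diary data.

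SAP 10.1.1.2 has three parts for the vomiting responder (V-SR):
- **Test:** the response proportions "will be analyzed by the Cochran-Mantel-Haenszel (CMH) test controlling for geographic region".
- **Rate difference:** "the difference in responder rates between the RLM and the placebo group and its corresponding 95% confidence interval", with neither an interval method nor a stratification stated.
- **Odds ratio:** "The Mantel-Haenszel estimate of odds ratio (RLM divided by Placebo) - controlling for geographic region", with its own 95% interval.

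Protocol Table 10-2, Responder row, has one bullet beginning "Risk differences and Wald CIs vs". The next bullet is a separate one, "Estimates derived from Cochran-Mantel-Haenszel (CMH) model controlling for factors (treatment group, region", and only the odds ratios and p-values stand under it. SAP 17.0 declares no changes from the protocol, so the Wald interval presumably carries over.

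SAP 10.2 says each symptom-responder endpoint "will be analyzed using the analysis method as described for the V-RS primary parameter", so five endpoints share the gap.

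**The concern.** The rate difference is the absolute effect that most readers will take from a responder endpoint. As laid out, it is the only between-group estimate in the primary analyses without region control. The CMH test and the odds ratio have it, and the DGSSS mixed model (SAP 10.1.1.1) has region as a fixed effect.

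When allocation is balanced within region, differences in response between regions contribute nothing to the error of the treatment difference. A crude Wald variance still counts them. The interval would then be wider than the design warrants when region is prognostic. Close to the significance boundary it could include zero while the stratified test is significant.

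**Working it through.** **Inputs from the documents.** 26% v 11% and 300 per arm (SAP 14.0); 1:1 allocation stratified by region (Protocol 7.3); seven regions (SAP 16.11); 2-sided 95% intervals (SAP 10.0); primary thresholds 0.025 and 0.0375 (SAP 10.3).

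**Assumptions, because the documents give no figures.** Region shares 10, 5, 20, 35, 12, 10 and 8%; exact 1:1 balance within region; between-region spread with SD 0, 0.5 or 1.0 on the logit scale; a borderline vomiting result of 17.5% v 11%; 50% v 42% for a symptom responder.

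**1. The plan's own figure.** The plan claims more than 90% power to reject at least one primary null. For vomiting alone at 0.025 (z = 2.241), the pooled SE is √(2 × 0.185 × 0.815 / 300) = 0.0317 and the unpooled SE is 0.0311. Then (0.15 − 2.241 × 0.0317) / 0.0311 = 2.54, which gives 99.4% power. With 240 per arm it is 97.9%. Vomiting alone at 0.025 is a lower bound for rejecting at least one null, so the claim is consistent. The DGSSS part cannot be rerun because Table 14-1 is not in the text. None of this uses the rate-difference interval.

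**2. Crude interval at the design rates.** SE = √[(0.26 × 0.74 + 0.11 × 0.89) / 300] = √(0.2903 / 300) = 0.0311. The half-width is 1.96 × 0.0311 = 6.1 points, so the interval is 15 ± 6.1, or 8.9 to 21.1 points.

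**3. What stratifying changes.** With exact balance within region, the Mantel-Haenszel difference equals the crude difference, so only the variance moves. In each arm, with region shares w and regional rates pᵢ,

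p(1 − p) = Σ w pᵢ(1 − pᵢ) + [Σ w pᵢ² − p²].

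The bracket is the between-region part, which stratifying removes.
- *SD 1.0.* Relamorelin rates are 7, 57, 11, 34, 47, 5 and 26%; placebo rates are 2, 29, 4, 14, 22, 2 and 10%. The brackets are 0.0918 − 0.2587² = 0.0249 and 0.0181 − 0.1099² = 0.0060, together 0.0309. The stratified SE is √[(0.2903 − 0.0309) / 300] = 0.0294, so the crude interval is 0.0311 / 0.0294 = 1.058 times as wide.
- *SD 0.5.* The brackets are 0.0748 − 0.2585² = 0.0080 and 0.0138 − 0.1087² = 0.0020, together 0.0100. The SE is √(0.2803 / 300) = 0.0306 and the ratio is about 1.018.

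**4. Simulation.** 200,000 trials per row, crude Wald against a Mantel-Haenszel-weighted interval with within-region variance, each compared with the CMH test at 0.05. All entries except SD are percentages.

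| Rates | SD | Crude excess width | Coverage crude / stratified | Crude: CMH significant, interval includes 0 | Crude: CMH not significant, interval excludes 0 | Stratified: same two disagreements |
|---|---|---|---|---|---|---|
| 26 v 11 | 0 | −0.2 | 94.83 / 94.91 | 0.00 | 0.01 | 0.00, 0.00 |
| 26 v 11 | 0.5 | 1.6 | 95.28 / 94.96 | 0.01 | 0.00 | 0.00, 0.00 |
| 26 v 11 | 1.0 | 5.7 | 96.11 / 94.96 | 0.03 | 0.00 | 0.00, 0.00 |
| 17.5 v 11 | 0 | −0.2 | 94.85 / 94.87 | 0.03 | 0.15 | 0.01, 0.17 |
| 17.5 v 11 | 0.5 | 1.2 | 95.23 / 94.94 | 0.81 | 0.00 | 0.02, 0.23 |
| 17.5 v 11 | 1.0 | 4.2 | 95.84 / 94.94 | 2.96 | 0.00 | 0.02, 0.23 |
| 50 v 42 | 0 | −0.2 | 94.66 / 94.81 | 0.00 | 0.91 | 0.06, 0.48 |
| 50 v 42 | 0.5 | 2.8 | 95.37 / 95.00 | 0.58 | 0.00 | 0.01, 0.24 |
| 50 v 42 | 1.0 | 10.9 | 96.87 / 95.02 | 7.05 | 0.00 | 0.01, 0.18 |

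At 26% v 11% the half-width falls from 6.1 points to 6.1, 6.0 and 5.8 as the spread grows. With equal rates of 11%, the CMH test rejects in 4.9 to 5.0% of trials.

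**5. With the Sato variance.** A separate run (6,000 replicates per setting, 26% v 11%, seven regions) gave a Sato SE of 1.000, 0.995, 0.980 and 0.961 times the Wald SE: no regional difference, then assumed placebo ranges of 7–16%, 4–22% and 2–29%. The inverses (1 / 0.995 = 1.005, 1 / 0.980 = 1.020, 1 / 0.961 = 1.041) make the crude interval 0 to 4% too wide. Sato coverage was 94.7 to 94.9%. In the two widest settings Wald coverage was 95.3 to 95.6%.

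**The case against.** A reader might infer that the plan prescribes an unstratified interval and that this interval is too wide. The documents support neither statement outright. The SAP sentence names no method. Wald comes from a generic protocol row that still holds a template placeholder, and a Mantel-Haenszel difference with a normal-theory interval is also of Wald type. Unstratified is the natural reading of both layouts, not a statement in either. The excess width depends on regional response rates that the documents do not give. It is nil if regions are alike, and the largest figures need a spread such as 2% to 29% on placebo.

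A reader might also infer that the trial's conclusion is at risk. It is not. Success is decided by the CMH p-value within the multiplicity procedure, and the rate difference enters no decision rule. A region-adjusted effect with an interval, the odds ratio, is already planned. At the design rates, a significant CMH test with an interval that includes zero occurs in at most 0.03% of trials.

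Two further limits stand. The calculations assume exact balance within region, while the available text gives no block size and the efficacy population is mITT. And SAP 4.0 says the full analyses no longer apply after early termination and that descriptive efficacy analyses are added. The available text does not show whether this interval will be produced.

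What remains is that the SAP does not state the interval method for a primary endpoint's absolute effect, and that the only method named elsewhere sits outside the region-controlled estimates.

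**Conclusion.** The point holds as a minor improvement in specification and precision. The rate difference and its interval should follow the stratification that the design, test and odds ratio already use, and the text does not say that they do.

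If the interval is crude, it errs on the conservative side. At the design rates the excess width is about 0% with no regional spread, 1.6% at SD 0.5 and 5.7% at SD 1.0, with coverage up to 96.1%. For assumed symptom-response rates of 50% v 42%, the excess reaches about 11% at the widest spread. A significant test beside an interval that includes zero becomes visible only in borderline results: up to 3.0% of trials at 17.5% v 11% and 7.1% at 50% v 42%, both at the widest assumed spread. Type I error, power and the formal decision do not change.

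Stratifying does not give full agreement. About 0.2 to 0.5% of borderline trials still disagree with CMH at 0.05. In addition, the primary tests use 0.025 and 0.0375 while the intervals are 95%. If the smaller primary p-value were 0.03, neither hypothesis would be rejected, yet the 95% interval for that endpoint would normally exclude zero.

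**What to change.** In SAP 10.1.1.2, state that the responder-rate difference is the Mantel-Haenszel risk difference stratified by geographic region (after any pooling under SAP 16.11) with its Sato 95% interval. Make the Responder row of Protocol Table 10-2 agree. The cross-reference in SAP 10.2 then covers the four symptom-responder endpoints. Apply this wherever the interval is still produced after termination. If the sponsor prefers a crude difference to match the crude percentages beside it, the SAP should say that it is unstratified.

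The cost is a phrase in each document and one software option (COMMONRISKDIFF in PROC FREQ). It needs no new data and no model that could fail to converge. In these calculations it costs essentially nothing when regions are alike and gains precision when they differ.

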10.1.2 Sensitivity Analysis for Missing data

Missing weekly DGSSS and missing number of weekly vomiting episodes will be imputed using multiple imputation (MI) approaches. MI will be performed under Missing at Random (MAR) and Missing not at random (MNAR) assumptions using the SAS/STAT procedures PROC MI and PROC MIANALYZE.

10.1.2.1 Sensitivity Analysis for Missing Data of Vomiting Study Responder

MI for V-SR will be performed under both MAR and MNAR assumptions. We will follow the steps below to generate datasets and analyze the data:

1. Imputed datasets generation
 - a) Missing at Random (MAR): The imputation of post baseline weekly values will be based on a multivariate normal distribution. In each imputation, a Monte-Carlo Markov chain (MCMC) method will be used to impute the missing values of post baseline weekly values from the observed data of the same group. The initial mean vector and covariance matrix for the MCMC will be obtained using an expectation–maximization algorithm.
 - b) Missing not at random (MNAR): The implementation of the pattern-mixture model with control-based pattern imputation of Ratitch and O’Kelly (2011) will be used to impute missing data under the MNAR assumption.
 - o Intermittent (non-monotone) missing data in both treatment groups are imputed using the MCMC method under the MAR assumption as described in Step 1- a.
 - o remaining monotone missing data are imputed using a pattern-mixture model approach using a sequential regression imputation model estimated based on data from the placebo arm only.

Imputed values for the number of weekly vomiting episodes will be restricted to ≥ 0 post imputation. 50 imputed datasets will be generated.

2. Calculate V-SR rate in the imputed datasets.
3. Model-based key estimates (odds ratio and standard error) will be obtained for V-SR for each imputed dataset using the same method as described in Section 10.1.1.2.
4. Take the log transformation for odds ratio ($\log(OR)$) and calculate standard error of transformed estimate ($SE(\log(OR))$) in each imputed dataset. $SE(\log(OR))$ is obtained from the log-transformed lower and upper confidence limits for the odds ratio estimate.
5. Output the combined $\log(OR)$, $SE(\log(OR))$, and p-values for all imputed datasets using PROC MIANALYZE.
6. Back transform the combined results of OR and SE and calculate 95% CI, by taking the exponentiation of the point estimates for $\log(OR)$ and for the lower and upper CI limits for $\log(OR)$ (Ratitch et al. ,2013).

10.1.2.2 Sensitivity Analysis for Missing Data of Change from Baseline in the Weekly DGSSS

MMRM analysis of change from baseline in the weekly DGSSS is based on the assumption of MAR and this approach uses available data including data from participants with partial data to estimate the mean treatment effect without filling in the missing data (Mallinchrod et al., 2008). Thus, MI for change from baseline in the weekly DGSSS will be performed only under MNAR assumption. The following steps will be followed to generate datasets and analyze the data:

1. Imputed datasets generation: Use the method as described in Step 1 Part b) in Section 10.1.2.1 to generate 50 datasets. Imputed values for change from baseline in the weekly DGSSS will be restricted to ≥ -40 and ≤ 40 .
2. Model based key estimates (LSMean difference between treatment group and standard error) will be obtained for the change from baseline to week 12 in the weekly DGSSS for each imputed dataset using the same method as described in Section 10.1.1.1.
3. Calculation of the combined mean difference, 95% CI, and p-value for the change from baseline to week 12 in the weekly DGSSS will be done using the method proposed by Rubin (1987) via PROC MIANALYZE.

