10.0 Efficacy Analyses

The efficacy analyses will be based on the mITT Population.

Most efficacy parameters will be derived from the DGSSD, a 7-item, patient-reported daily diary designed to assess the severity of 6 core signs and symptoms of DG—nausea, abdominal pain, postprandial fullness, bloating, vomiting, and early satiety—and the frequency of vomiting episodes (Appendix 1). For purposes of the analyses, weekly values will be calculated from the daily e-diary data as described in Section 16.3 of this SAP. For weeks with less than 4 days of available DGSSD data, weekly values will be set to missing.

Baseline values for parameters are derived from the DGSSD collected in the Run-in period, (ie, *Diabetic Gastroparesis Symptom Severity Score (DGSSS: sum of nausea, abdominal pain, postprandial fullness, and bloating), nausea, abdominal pain, postprandial fullness, bloating, early satiety, vomiting frequency and vomiting severity*) following the steps below:

- Weekly value for Week -2 and Week -1 will be the average value of DGSSD in the week (See the analysis week definition for Week -2 and Week -1 in Section 16.2.1);
- Baseline will be the average of the two weekly values of Week -2 and Week -1.

All statistical tests will be 2-sided hypothesis tests performed at the 5% level of significance for main effects. All confidence intervals will be 2-sided 95% confidence interval, unless stated otherwise.

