10.1 Primary Efficacy Parameters

There are two primary efficacy parameters in each study as follows:

- a) **Change from Baseline to Week 12 in the weekly DGSSS:** Baseline is the average of the 2 weekly DGSSS from the 2-week, placebo Run-in Period.
- b) **Vomiting Study Responder (V-SR):** A Vomiting Study Responder is defined as a participant with zero weekly vomiting episodes during each of the last 6 weeks of the 12-week Treatment Period.

In this study, the primary efficacy analysis (see Section 10.1.1 below) is said to have achieved the primary study objective if it indicates that relamorelin is superior to placebo for testing on at least one of the two primary efficacy parameters (following the specified multiplicity testing procedure as described in Section 10.3).

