14.0 Determination of Sample Size

The sample size and statistical power for the DGSSS endpoint was assessed by simulation. Data were simulated for the DGSS over time under the assumption of a multivariate normal distribution and based on mean responses in Study RM-131-009 variance -covariance structure ([Table 14-1](#)). A missing completely at random (MCAR) dropout rate of 20% by Week 12 was assumed for each treatment.

Vomiting response rates were assumed to be those observed in Study RM-131-009 (26% and 11% for treatment and placebo respectively). Sample size was assessed using the POWER procedure in SAS.

The sample size of approximately 300 participants per arm will provide more than 90% power to reject at least one of the primary null hypotheses using the multiplicity approach described in [Section 10.3](#).

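### The MAR imputation check on vomiting response draws weekly counts from a floored normal model, so too few dropouts become responders; if relamorelin dropout is higher, its agreement with the non-responder rule says little

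*SAP*

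**What the plan says.** SAP 10.1 sets a strict endpoint: "A Vomiting Study Responder is defined as a participant with zero weekly vomiting episodes during each of the last 6 weeks". SAP 10.1.1.2 makes a participant a non-responder if "the weekly number of vomiting episodes is missing for any of the last 6 weeks of the 12-week Treatment Period". SAP 10.1.2.1 then tests that rule by multiple imputation, with 50 datasets.

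- MAR version: "The imputation of post baseline weekly values will be based on a multivariate normal distribution", by MCMC within the same treatment group.
- MNAR version, intermittent gaps: "Intermittent (non-monotone) missing data in both treatment groups are imputed using the MCMC method under the MAR assumption".
- MNAR version, remaining monotone gaps: "imputed using a pattern-mixture model approach using a sequential regression imputation model estimated based on data from the placebo arm only". No distribution is named for this step.
- Both versions: "Imputed values for the number of weekly vomiting episodes will be restricted to ≥ 0 post imputation". The V-SR rate is calculated next, and log odds ratios are pooled.

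No rounding, count model or binary model appears in the text available. SAP 10.0 says that "weekly values will be calculated from the daily e-diary data as described in Section 16.3 of this SAP"; Section 16.3 is not in that text, so a rounding rule there cannot be excluded. For dropout, SAP 14.0 says: "A missing completely at random (MCAR) dropout rate of 20% by Week 12 was assumed for each treatment". This is stated for the DGSSS simulation and agrees with the 240 of 300 completers per arm in Protocol 5.2.

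**The concern.** Weekly vomiting counts have many zeros and a long right tail. A normal model fitted to them has a positive mean and a large spread, so a draw at or below zero is far from certain even for someone who has not vomited so far. V-SR needs this in every missing week of Weeks 7-12: six weeks for a dropout before Week 7, one to five for a later one. Because stopping treatment also ends participation (Protocol 8), dropout is the main source of missing weeks.

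The MAR check is there to show what would happen if dropouts had responded like the rest of their own arm. If it turns nearly all of them into non-responders, it largely repeats the primary rule. Agreement between the two could then be reported as robustness when it partly follows from the imputation model.

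**Working it through.** **The plan's own figure.** SAP 14.0 claims more than 90% power to reject at least one primary null hypothesis. For vomiting alone, 26% against 11% with 300 per arm at two-sided 0.025 gives 99.4%. With 20% dropouts counted as non-responders (0.8 × 26% = 20.8%, 0.8 × 11% = 8.8%) it gives 97.3%. The claim stands.

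**Inputs from the documents.** 26%/11% response, 300 per arm and 20% MCAR dropout (SAP 14.0); zero in each of Weeks 7-12 (SAP 10.1); floored normal draws (SAP 10.1.2.1).

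**Assumed.** Weekly count ~ Poisson(exp(a + trend + u + e)), with patient effect u, weekly AR(1) error e, and at least one run-in episode for entry. The last observed week is uniform on 1-11. Models A-C vary the between- and within-patient spread. In model D, 24%/9% of patients stop vomiting after Weeks 1-6. All four are set to 26%/11%. The floor is read as setting negative draws to zero.

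**Fit to Phase 2b.** Protocol 3.2 reports vomiting reductions of about 75% on relamorelin and 70% on placebo. Models A-C give about 85-87% and 63-64%; model D gives about 72-73% and 67%. Model D is the closest.

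**Dropouts imputed as responders, 20%/20% dropout.**

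| | Relamorelin | Placebo |
|---|---|---|
| Own-arm truth | 26% | 11% |
| SAP MAR, models A-D | 4-8% | 2-6% |
| SAP MAR with rounding | 7-11% | 4-7% |
| Logistic MAR | 20-26% | 8-11% |

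Repeat runs widen the relamorelin figures to about 3-8%, and to about 7-12% with rounding. Model D gives about 5%. A separate set of gamma-Poisson, declining-rate and remission models gave 3.0-5.5% against 25-30% true. When only one week is missing, 45-49% of truly all-zero relamorelin patients are recovered (54-68% with rounding).

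**Effect on the odds ratio (ranges over A-D; unequal dropout is assumed).**

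| Dropout, relamorelin/placebo | Own-arm | Non-responder | SAP MAR | Log-OR gap closed |
|---|---|---|---|---|
| 20%/20% | 2.82-2.96 | 2.71-2.84 | 2.59-2.81 | little gap to close |
| 25%/15% | 2.79-2.89 | 2.31-2.40 | 2.37-2.43 | 4-14% |
| 30%/10% | 2.79-2.93 | 2.00-2.10 | 2.14-2.25 | 14-21% |
| 10%/30% | 2.81-2.91 | 3.65-3.80 | 3.00-3.47 | 25-78% |

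Taking all runs together, the ranges are about 4-25% with higher relamorelin dropout and about 22-82% with higher placebo dropout.

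**Hand check.** Let d be the dropout fraction, p the true response and r the share of dropouts imputed as responders. The arm's rate is (1 − d)p + dr. Use one model A run: r = 3.6% relamorelin, 2.2% placebo.

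- Own-arm: (0.26/0.74)/(0.11/0.89) = 2.84.
- 30%/10%, non-responder: 0.7 × 0.26 = 0.182 and 0.9 × 0.11 = 0.099, OR 2.02.
- 30%/10%, SAP MAR: 0.182 + 0.3 × 0.036 = 0.1928 and 0.099 + 0.1 × 0.022 = 0.1012, OR 2.12. Gap closed: ln(2.121/2.025)/ln(2.843/2.025) = 14%.
- 10%/30%: non-responder 0.234 and 0.077, OR 3.66; SAP MAR 0.2376 and 0.0836, OR 3.42. Gap closed: ln(3.662/3.416)/ln(3.662/2.843) = 27%.
- 20%/20%: non-responder OR 2.72, SAP MAR 2.69, own-arm 2.84.

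**If dropout is not MCAR.** Suppose a week with vomiting carries five times the dropout hazard (assumed). True response among dropouts falls to 13-15% on relamorelin and 5-6% on placebo, against 2-4% and 1-5% imputed. The relamorelin shortfall roughly halves.

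**The case against.** The strongest case is about consequence. The plan assumes equal dropout, and the odds ratio then barely moves by any method. Protocol 3.2 gives little sign of imbalance at this dose: 3 adverse-event discontinuations at 10 µg against 3 of 104 on placebo. SAP 10.1 and 10.3 rest success on the primary tests, and nothing depends on this check. SAP 4.0 says that the planned full analyses no longer apply after early termination. All of this stands and limits the weight of the point. It does not make the imputation model suitable.

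Three stronger readings are tempting and are not supported.

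- **That the check fails whichever arm loses more participants.** With higher placebo dropout, where the non-responder rule overstates the effect, the check moves part of the way. With higher relamorelin dropout, where it stays close to the primary rule, that rule is already conservative.
- **That about 16 relamorelin and 7 placebo responders are lost among 60 dropouts per arm.** Those are the expected totals (60 × 0.26 = 15.6; 60 × 0.11 = 6.6), not the loss, and they need MCAR. Protocol 8 lists lack of efficacy as a discontinuation reason.
- **That the control-based version is equally affected.** Its monotone step names no distribution. Read as normal, it gives 4-9% of relamorelin dropouts as responders against a control-based benchmark of 15-17%, but the odds ratios at 20%/20% are close (2.63-2.83 against 2.53-2.58).

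A rounding rule in Section 16.3 is possible but would not cure the shortfall. If negative draws were redrawn instead of set to zero, almost no imputed week would be exactly zero, which is worse.

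**Conclusion.** The concern holds as a minor point about the plan as written. The floored normal model under-imputes runs of zeros: about 3-8% of relamorelin dropouts are imputed as responders against about 26% true under MCAR, and about 5% in the model closest to Phase 2b. The consequence depends on the direction of any dropout imbalance. With higher relamorelin dropout, agreement between the MAR check and the primary rule is weak evidence. With higher placebo dropout, the check is incomplete but informative. At equal dropout there is almost nothing to detect.

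A reader might infer that the primary vomiting result or the sample size is in doubt. Neither is: the primary test does not use this imputation, and the power figure reproduces. The size of the shortfall rests on assumed count models, dropout timing and MCAR; its direction was the same in every model tried.

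**What to change.** In Step 1 of SAP 10.1.2.1, replace the normal draws with logistic imputation of a weekly indicator, any vomiting (yes/no). Use sequential logistic regression for monotone gaps and fully conditional (FCS) logistic regression for intermittent gaps. Predictors are the earlier weeks, or a summary of them, and baseline vomiting frequency, with an augmented fit if separation occurs. Fit within arm for the MAR version and from the placebo arm for the control-based version. Derive V-SR from the indicators and keep the pooling in steps 3-6.

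The sequential form was tried with the last two weeks, the share of earlier weeks with vomiting and log(1 + baseline) as predictors. At 25%/15% it gave an odds ratio of 2.71-2.86 against own-arm 2.79-2.89; at 30%/10%, 2.61-2.91 against 2.79-2.93.

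The cost is SAP wording and a little more programming, with no new data. The size of the counts is no longer used. Some under-imputation remains if vomiting stops abruptly (model D: 20% against 26% own-arm, 11% against 17% control-based). The FCS step for intermittent gaps was not simulated.
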